 - Hypothesis: The mean self-reported pain level using a 10-point numeric pain scale will be a minimum of 1 point lower in patients receiving VR compared to those in the control group.

Secondary Aims:

- To determine if VR reduces the total amount of inpatient narcotic use in the acute post-operative period (until discharge) following spinal deformity surgery.
 - Hypothesis: Patients receiving VR will have reduced total inpatient narcotic administration during their hospital stay compared to those in the control group.
- To determine if VR can facilitate earlier mobilization following spinal deformity surgery.

- Hypothesis: Patients receiving VR will participate in a fewer number of physical therapy (PT) sessions prior to receiving clearance for discharge by PT staff.

Outcome Definitions/Data Points Collected

Primary Outcome:

Pain will be measured through the 10-point numeric pain scale self-reported by the patient (patient's will be between 13-18 years of age).

Secondary Outcomes:

- Mobilization will be assessed by the number of PT sessions prior to receiving clearance for discharge by PT staff.
- Patient post-operative gross motor activity level will be measured via wearable Fitbit
- Opioid utilization will be assessed by calculating the total inpatient dose of opioids administered (as documented in the EMR) during the post-operative period.
- Side effects from virtual therapy, including headaches, vertigo, and nausea

Data collected:

- Patient demographics
 - Age, Sex, Race, Language, Ethnicity
- Patient Past Medical History
- Patient medication/drug history (prescription and recreational)
- Prior experience with VR
- Surgical details
 - # of spinal levels involved in fusion
 - Duration of surgery
 - Surgical blood loss
 - Need for transfusion
 - Complications
- Radiographic imaging
- 10-point numeric pain scale ratingsPhysical Therapy notes
 - Number of sessions prior to discharge clearance, timing of sessions, duration of each session, comments from each session,
- EPIC Medication History
- Length of stay
- Timing and duration of virtual reality sessions
- Side effects from virtual therapy sessions
 - Seizures
 - Loss of awareness
 - Headaches
 - Vertigo
 - Nausea
 - Eye strain / blurred or double vision
 - Eye or muscle twitching

- Involuntary movements
- Dizziness and lightheadedness
- Disorientation
- Impaired balance and hand-eye coordination
- Excessive sweating
- Increased salivation
- Drowsiness
- Fatigue
- Motion sickness

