All pediatric patients (ages 13-18) undergoing corrective scoliosis surgery at Connecticut Children's over a span of 12 months (03/01/24-03/01/25) will be approached by a study team member during the pre-operative stage with information and consent documentation about the study. If the patient acknowledges that they are interested and would like more information, then the study team member will complete the formal consent and HIPAA process with the patient and family. This will take place in a private setting, and the patient/family will be given ample time to read the consent and have any questions answered. As a part of the consent and HIPAA, patients will consent to the study procedures as well as the research study team accessing their medical record for data collection. Each patient's MRN will be entered into a secure password protected Excel enrollment log and be given a subject identification number for de-identification. During the consenting procedure, the patient will utilize the VR device for 5 minutes to screen for side effects and become accommodated to the device. In the event that the patient experiences side effects during this 5-minute period, they will be excluded from the study.

Retrospective chart review sample:

The retrospective chart review is intended to be used as a historical control to the prospective arm of the study. All patients in the retrospective time frame (02/01/19 - 02/01/24) will be identified using CPT codes (fusion codes: 22800, 22802, 22804 and instrumentation codes: 22842, 22843, 22844) as well as ICD-10 Code M41.* from Slicer Dicer. These patient's charts will be verified by a study team member to ensure they meet inclusion criteria, and then they will be entered into a using a secure password protected Excel enrollment log. Each patient's MRN will be recorded into the enrollment log and will be given a subject identification number for de-identification. Patients in this cohort will not be approached for consent as we will not collect identifiable information and only their deidentified medical record will be in review. It is also likely that some patients are no longer clinically active at Connecticut Children's, and therefore we would not be able to contact these patients for consent.

Study Retention/Withdrawal

Prospective Cohort:

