
Retrospective Arm:

Eligible patients verified for the retrospective chart review will be entered into a secure Excel enrollment log and be deidentified by using a subject identification number. The MRN and subject ID will be entered into a linking file that will be password protected and only accessible to authorized study personnel. The following information will be collected from the patient charts: demographics, degree of scoliosis, surgical details, PT notes, pain medication regimens, associated pain scales, and relevant follow up notes. These data will be entered into REDCap in a de-identified manner and will only be accessible to authorized study team members.

Sample Size Justification

This study will utilize a convenience sample of patients presenting to Connecticut Children's for a scoliosis surgery within the study timeframe.

Feasibility, Accrual, and Duration of Accrual

Accrual will occur over a 12 month period (03/01/24 - 03/01/25). Approximately 60-80 patients undergo a surgical procedure for the correction of scoliosis annually at Connecticut Children's. We estimate ~40% will decline to participate, therefore we anticipate approximately 35-50 patients being included in the prospective arm of study. For the retrospective arm of the study, we approximate to include 350 patients for chart review.

Study Limitations

This study is limited in that we are only assessing the utility of VR to reduce pain in a specific patient population (pediatric patients undergoing surgical correction of scoliosis), at a specific time (the immediate post-operative period), at a single institution (Connecticut Children's), and within a relatively small sample size, which limits the generalizability of the study to apply to other patient populations. This study is also limited in that it utilizes a retrospective chart review as a historical control. By collecting data retrospectively, it is likely that the study team will encounter missing variables and will not be able to categorize pain as accurately as they would be able to in a prospective or true randomized control trial study designs.

Data Analysis

- Intention to treat analysis
- A biostatistician will assist in analysis
- Descriptive statistics (frequency, percentage, mean, standard deviation, median, and interquartile range) will be utilized to describe the two groups (VR and control)

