- Fisher's Exact test, independent t-tests, and Wilcoxon Rank Sum tests will be used for univariate analysis to compare demographics between the two groups (VR and control)
- Pain outcome:
 - Univariate analysis using independent t-tests or Wilcoxon rank sum tests will be used to compare the daily mean pain scales
- Opioid utilization outcome
 - Univariate analysis using independent t-tests or Wilcoxon rank sum tests will be used to compare the total inpatient dose of opioids administered

Administrative Organization/Roles and Responsibilities

- Principal Investigator - [name] - Connecticut Children's Division of Neurosurgery
- Co-Principal Investigator – [name] – UConn Department of Psychological Sciences
- Co-Principal Investigator – [name] – Connecticut Children's Division of Orthopedic Surgery
- Co-Principal Investigator – [name] MPH – Connecticut Children's Division of Pain and Palliative Medicine
- Student Coordinators and Responsibilities:
 - [name] – Study Coordinator
 - Study Design

- Data quality
- Data analysis
- Project management
- Manuscript drafting
- [name] – Medical student
 - Study design
 - Study Procedures
 - Data analysis
 - Manuscript drafting
- [name] – Medical Student
 - Study Design
 - Study procedures
 - Data analysis
 - Manuscript drafting

Use of Study Results

The data generated from this study will be used to re-evaluate the postoperative pain management pathway for pediatric patients in the post-operative period following spinal deformity surgery. These data will also be used for presentations / publications.

Study Budget

Item	Quantity	Per
VR Computer	1	\$3,100
VIVE Wireless Head Mounted Display	1	\$1,100
Cleanbox	1	\$2,000
Computer supplies (external hard drives, batteries, sanitizer wipes)	1	\$200
VR Software	1	\$500
TOTAL		\$6,900

References:

1. Janicki, J.A. and B. Alman, *Scoliosis: Review of diagnosis and treatment*. Paediatr Child Health, 2007. **12**(9): p. 771-6.

2. Al-Mohrej, O.A., S.S. Aldakhil, M.A. Al-Rabiah, and A.M. Al-Rabiah, *Surgical treatment of adolescent idiopathic scoliosis: Complications*. Ann Med Surg (Lond), 2020. **52**: p. 19-23.
3. Sung, S., et al., *Incidence and Surgery Rate of Idiopathic Scoliosis: A Nationwide Database Study*. Int J Environ Res Public Health, 2021. **18**(15).

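### Operating surgeon and service are not among the listed surgical details, and the comparison with historical controls is unadjusted, so any difference in surgeon mix between the arms would enter the VR effect unseen

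*Combined protocol and SAP*

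**What the plan says.** **Data list.** Outcome Definitions/Data Points Collected itemises the surgical details: the number "of spinal levels involved in fusion", then "Duration of surgery", blood loss, need for transfusion, and complications. Surgeon and service are not named.

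**Chart abstraction.** For both arms, Study Procedures gives only a general list: "demographics, degree of scoliosis, surgical details, PT notes, pain medication regimens, associated pain scales, and relevant follow up notes". Appendix A is named as the data collection tool, but its content is not in the available text.

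**Design.** Sampling Method/Recruitment Process states: "The retrospective chart review is intended to be used as a historical control to the prospective arm of the study". The control window is five years. Its start and end are given as March under Inclusion/Exclusion Criteria and as February under Sampling Method/Recruitment Process, but its length is the same. The VR cohort is recruited over the following 12 months.

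**Analysis.** Data Analysis plans t-tests or Wilcoxon rank sum tests for daily mean pain and for total opioid dose. It names no covariate. It lists no test for PT sessions, although that outcome has its own hypothesis.

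**Leadership.** Under Administrative Organization/Roles and Responsibilities, the principal investigator belongs to "Connecticut Children's Division of Neurosurgery" and one co-principal investigator to "Connecticut Children's Division of Orthopedic Surgery". The other two are in psychological sciences and in pain and palliative medicine.

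**The concern.** The arms are separated by calendar time, not by randomisation. Staff turnover or a change in how cases are allocated would therefore line up with the treatment contrast. The VR arm is also self-selected, with about 40% expected to decline, and in a group of 35-50 a modest imbalance in uptake can move the mix noticeably.

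Surgeon or service can plausibly affect technique, analgesic ordering and mobilisation routine. These bear on pain, opioid dose and PT sessions to clearance, the three outcomes set against the controls. Study Procedures describes the controls as having had the same operation, but the listed variables cannot show whether the same surgeons or services treated both groups. Study Limitations acknowledges missing variables and less accurate pain data in the retrospective arm. It does not mention surgeon, service or change in practice over time.

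**Working it through.** **1. Arm sizes, from the plan's own figures (Feasibility, Accrual, and Duration of Accrual).**

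- VR arm: 60-80 operations a year × (1 − 0.40) = 36-48, against the stated 35-50.
- Controls: 5 years × 60-80 = 300-400, midpoint 350, against the stated 350.

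Both reproduce closely enough. I use 35 or 50 VR patients and 350 controls.

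**2. Form of the bias.** Take two services with mean pain differing by d points, and let s be the share of one service among VR patients minus its share among controls. With no true VR effect, the unadjusted difference in means is expected to be

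bias = d × s.

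The documents give neither d nor s. Both are assumptions below, and either sign is possible.

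**3. Effect on a two-sided 5% test.** The plan states no significance level and no standard deviation. Assuming SD = 2 points in both arms:

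- 35 VR patients: SE = 2 × √(1/350 + 1/35) = 0.355
- 50 VR patients: SE = 2 × √(1/350 + 1/50) = 0.302

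False-positive rate = Φ(bias/SE − 1.96) + Φ(−bias/SE − 1.96), which is the same for either sign of the bias.

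| d (assumed) | Shift s (assumed) | Bias, either direction | Rate, 35 VR | Rate, 50 VR |
|---|---|---|---|---|
| any | 0 | 0 | 5% | 5% |
| 0.5 | 20 points | 0.1 | 5.9% | 6.3% |
| 1 | 20 points | 0.2 | 8.7% | 10.1% |
| 1 | 30 points | 0.3 | 13.5% | 16.8% |
| 1 | 50 points | 0.5 | 29.2% | 38.0% |

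The only benchmark in the plan is the primary hypothesis of at least 1 point, so a 0.2-point bias is 20% of it. A bias in VR's favour would inflate the effect; one in the other direction would mask part of a real one.

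**4. Could a listed variable stand in for surgeon?** Fused levels, operating time and blood loss capture part of technique. Medication history and PT notes record what was given and done after surgery, but opioid dose and PT sessions are themselves outcomes and can be affected by VR. They cannot serve as baseline adjusters in place of surgeon.

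**The case against.** The strongest reply is that the premise is inferred. From the two surgical affiliations, a reader might conclude that both divisions operate on these patients and that their shares changed. The documents say neither: they give investigators' departments, not who operates. Nor do they tie refusal to service, since every eligible patient is to be approached and offered VR. The background also describes multimodal analgesia and daily PT as institution-wide practice, which would narrow differences between services. All of this stands, and it is why no particular size or direction of bias can be claimed. It does not remove the point, because surgeon mix can drift over six years even within one service.

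A reader might also infer that surgeon is definitely not collected, or could never be recovered. Neither is supported. Appendix A may hold such a field. Record numbers are logged for both arms and a linking file is kept for the controls, so the field can be abstracted while that linkage exists.

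Finally, the larger weakness is that the analysis adjusts for nothing, so a surgeon field alone would change no planned result. That is right, and the field is worth adding only together with an adjusted comparison. Equally, if Appendix A already collects surgeon, the planned tests would still ignore it.

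**Conclusion.** The point holds in a limited form, as a cheap improvement. The listed surgical details omit surgeon and service, and the planned tests would pass any difference in mix straight into the VR contrast. Whether such a difference exists is not known from the documents.

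On assumed inputs, the bias runs from zero with no shift, through 0.1-0.2 points for a 20-point shift, to 0.5 points for a 50-point shift with a 1-point service difference. The smaller of these values lie below one standard error of the contrast (0.30-0.35 points at an assumed SD of 2). It would be wrong to read the figures as evidence that VR will look better than it is: the sign is open, and the service difference and shares have no source in the plan.

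**What to change.** 1. Add coded operating surgeon and service to the listed surgical details and to the REDCap form, in both arms, during abstraction. If Appendix A already has the field, list it in the protocol as well.
2. Tabulate surgeon and service mix by arm.
3. Pre-specify an adjusted comparison of pain, opioid dose and PT sessions, with service (or grouped surgeon where numbers allow) as a covariate or stratum, alongside the baseline and surgical variables already collected.
4. Optionally, add a sensitivity analysis restricted to surgeons who contribute patients to both arms.

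**Cost.** One coded field per chart, in records already opened for fused levels and blood loss, and a few degrees of freedom. With 35-50 VR patients, individual surgeon cells will be sparse, hence service or grouped surgeon. The optional restriction sets some controls aside. None of this removes other changes over calendar time, which remain a limitation of the historical control and should be stated as one.

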Scoliosis is broadly defined as deviation of the normal vertical alignment of the spinal column. Scoliosis is typically classified as congenital, neuromuscular, syndromic, or idiopathic and may be treated with observation, bracing, or surgical correction, depending on the severity and the clinical status of the patient.[1] Idiopathic scoliosis represents the most common pediatric subtype and has a prevalence of 0.5 – 5.2%, with an operative rate ranging from 3.9 – 9.8 operations per 100,000 members of the general population.[2-4] Post-operative pain following the surgical correction of pediatric scoliosis is inevitable and must be well managed to achieve the goals of patient comfort, early mobilization, and early discharge. As a result of the short- and long-term adverse effects of opioid use in the pediatric population, many practices are adopting multimodal pain management strategies to reduce the reliance on opioid analgesia.[5, 6]

Virtual reality (VR) has been extensively studied in regards to its ability to reduce peri-procedural pain and anxiety in a pediatric population.⁷ Non-pharmacological methods of distraction are a well-established method of pain control. Virtual reality, by providing a more interactive and immersive experience, has the potential to out-perform other distraction techniques. However, the specific impact of VR following scoliosis surgery has yet to be assessed.⁸ At Connecticut Children's, patients undergo multimodal pain management following scoliosis correction, including narcotics, muscle relaxants, anti-inflammatories, and gabapentin. Patients are also expected to participate with physical therapy daily. In the present study, we intend to investigate the effect of VR on subjective post-operative pain, total inpatient narcotic administration, and mobilization with physical therapy.

Research Question

Does implementation of VR reduce pain, reduce total narcotic administration, and increase mobilization with physical therapy in the immediate post-operative period following spinal deformity surgery in the pediatric population?

Primary and Secondary Aims

Primary Aim(s):

- To determine if virtual reality (VR) reduces the subjective perception of pain for pediatric patients in the acute post-operative period (until discharge) following spinal deformity surgery.

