- Skin irritation
- Low temperature burns
- Hair loss
-

Study Design

Mixed methods with a prospective cohort and retrospective chart review.

Target Population

Pediatric patients (ages 13-18) undergoing corrective scoliosis surgery at Connecticut Children's over a span of 12 months (03/01/24-03/01/25).

Inclusion/Exclusion Criteria

Inclusion:

Prospective:

- All pediatric patients (ages 13-18) at Connecticut Children's undergoing surgical correction for idiopathic scoliosis over a span of 12 months (03/01/24-03/01/25) will be eligible for inclusion in the prospective arm.

Retrospective:

- All pediatric patients (ages 13-18) at Connecticut Children's that underwent surgical correction for idiopathic scoliosis in the retrospective time frame (03/01/19 - 03/01/24) will be eligible for inclusion in the retrospective arm.

Exclusion:

- History of seizures
- Cognitive developmental delay precluding participation in VR
- Head or neck surgery that does not allow a head-mounted display to be worn safely
- Chronic pain requiring the daily use of opioids for more than 2 weeks prior to the procedure
- Non-English speakers
- Side effects during screening
- Patients with vagal nerve stimulators, cardiac pacemakers, and/or cochlear implants that may receive interference from the VR device

Sampling Method/Recruitment Process

Prospective cohort sample:

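### Five years of historical controls are compared with one later VR year by unadjusted tests, so drift in post-operative pain care could inflate or mask the VR difference unseen

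*Combined protocol and SAP*

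**What the plan says.** - **Control window.** Under Inclusion/Exclusion Criteria, patients aged 13-18 "that underwent surgical correction for idiopathic scoliosis in the retrospective time frame (03/01/19 - 03/01/24) will be eligible for inclusion in the retrospective arm". The Sampling Method section gives a window one month earlier: "All patients in the retrospective time frame (02/01/19 - 02/01/24) will be identified using CPT codes".
- **VR window.** Target Population and the accrual section both give 03/01/24 to 03/01/25. It does not overlap the control window.
- **Role of the controls.** "The retrospective chart review is intended to be used as a historical control to the prospective arm of the study". There is no concurrent control; Study Procedures gives low surgical volume as the reason for not randomising.
- **Analysis.** Data Analysis lists independent t-tests or Wilcoxon rank sum tests for daily mean pain and for total inpatient opioid dose. It plans no covariate, weight, stratum, time term, restriction to recent controls or sensitivity analysis. No test is listed for physical therapy (PT) sessions.
- **Limitations.** "This study is also limited in that it utilizes a retrospective chart review as a historical control". The consequences named are missing variables and less accurate pain categorisation. Change in care over time is not named.
- **Background.** "many practices are adopting multimodal pain management strategies to reduce the reliance on opioid analgesia". The hospital's own multimodal regimen is described without a start date and without saying whether it stayed constant over 2019-2024.

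**The concern.** Every control was operated on before every VR patient. An unweighted two-sample test on all eligible controls gives a 2019 patient the same weight as one from early 2024. If pain scores or opioid doses were already changing before March 2024, the test reports that change as part of the VR difference.

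Adjusting for age or number of levels fused would not remove this, because the source would be a change in care and not in patients. Pain medication regimens are abstracted in both arms, but no planned analysis uses them or the date of surgery to look for such a change.

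The results are meant to inform a re-evaluation of the hospital's post-operative pain pathway, so a difference that belongs to the period and not to VR could affect that decision.

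**Working it through.** **Inputs from the documents.** Control window of five years ending 03/01/24; VR window 03/01/24 to 03/01/25; "Approximately 60-80 patients undergo a surgical procedure for the correction of scoliosis annually at Connecticut Children's"; about 40% expected to decline; 35-50 VR patients and about 350 controls expected; hypothesised difference of at least 1 point.

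**Assumptions.** The documents give no SD, alpha or drift rate. I take SD 2 points (range 1.5-2.5), two-sided 0.05, surgeries spread evenly over each window, and the drift rates shown below.

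**Reproducing the plan's numbers.** 60-80 × 0.60 = 36-48, against 35-50 stated. 5 × 70 = 350, as stated. The central VR number used here is 70 × 0.60 = 42.

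**Gap between windows.** The midpoints are about 08/30/21 and 08/30/24, a gap of 3.0 years (3.08 with the 02/01 dates). Under linear drift, bias = d × 3.0. A single change of size S at the end of year k of the control window gives bias S × k/5; for example, 0.6 S if it came after year 3.

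**Pain, no VR effect.** SE = 2 × √(1/42 + 1/350) = 2 × 0.163 = 0.327. The false-positive rate is Φ(bias/SE − 1.96) + Φ(−bias/SE − 1.96).

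| Assumed fall per year | Bias | False-positive rate | Range (35-50 VR, SD 1.5-2.5) |
|---|---|---|---|
| 0.05 | 0.15 | 7.4% | 6-10% |
| 0.1 | 0.30 | 15% | 10-26% |
| 0.2 | 0.60 | 45% | 27-75% |

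Drift the other way masks an effect: if pain rose by 0.1 or 0.2 a year, a true 1-point benefit would appear as 1 − 0.3 = 0.7 or 1 − 0.6 = 0.4 points.

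**Opioid dose.** Assumed falls of 2%, 5% and 8% a year give false reductions of 1 − 0.98³ = 6%, 1 − 0.95³ = 14% and 1 − 0.92³ = 22%.

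**Controls from the last 24 months.** 350 × 2/5 = 140 controls; the gap is 1.5 years, so linear bias halves. The SE ratio is √(1/42 + 1/140) / √(1/42 + 1/350) = 0.176/0.163 = 1.08. At falls of 0.1 and 0.2 a year the false-positive rates drop to 7.1% and 13.7%. Power for 1 point is 81%, against 86.5% with all 350.

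**All controls with a linear time term.** In a model with intercept, group and surgery time, the variance of the group effect rises by a factor of 1.46, so the SE rises by √1.46 = 1.21 (0.327 to 0.394). Power for 1 point is 72%. Over 35-50 VR patients and SD 1.5-2.5, power is 48-95% with the time term and 62-99% without it.

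**The case against.** The strongest reply is that no drift has been shown. That is correct. A reader might take the Background sentence as evidence of a trend in this trial's outcomes, but it describes practices in general. For this hospital the documents describe a regimen and no change in it.

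A reader might also infer that any drift would favour VR. The Background suggests a direction for opioids at most and none for pain, the primary outcome; rising pain would hide a benefit.

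Nor do the documents support a drift large enough to produce the whole hypothesis. That needs 1/3.0 = 0.33 points a year, or about 1.7 points across the five control years, a rate obtained by working backwards from the 1-point target. For PT sessions, no comparison is specified, so there is no planned test to call biased.

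The sponsor can add that confounding with time comes with any non-concurrent control, that the historical control is disclosed, and that low volume is given as the reason. This explains the choice of a historical control. It does not explain pooling five years without regard to date, or leaving time trends out of the limitations.

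The remedies have limits too. The 24-month cut is a judgement and only reduces bias. A linear term removes only linear drift, extrapolates it into the VR year and costs power. Neither separates VR from a change that began when VR did.

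**Conclusion.** The concern holds as a weakness of the planned analysis, not as evidence of a trend. The plan cannot tell drift from a VR effect and includes no analysis that would reveal drift. The bias is about three times the yearly drift, in either direction. Modest assumed falls of 0.1 to 0.2 pain points a year raise the false-positive rate from 5% to about 15-45% in the central case.

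The 3.0-year gap follows from the documents. The drift rates, SD, significance level and even spread of surgeries are assumptions. The 350 controls equal the full five-year surgical volume before the age, diagnosis and exclusion criteria are applied, so the actual number may be lower. That changes the standard errors but not the bias.

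A reader might go further and hold that an effect lost after trend adjustment is not due to VR. That does not follow: at SD 2 a true 1-point effect would miss significance about 28% of the time in the time-adjusted model. Nor would analysing within the medication regimen settle the matter, because the regimen includes narcotics and opioid dose is an outcome.

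**What to change.** 1. Carry surgery date, or months before VR start, into the analysis dataset. It is not among the listed data items and the retrospective records are de-identified, so the protocol should specify it. It is needed in any case to select the controls.
2. Show pain and opioid dose by surgery year among controls.
3. Pre-specify two analyses beside the pooled test: (a) controls from the last 24 months before VR start; (b) all controls with a calendar-time term, described as removing linear drift only and as extrapolating into the VR year. Do the same for PT sessions if they are compared.
4. Add change in care over time to Study Limitations, and state that a change coinciding with VR start cannot be separated from VR.
5. State that conclusions will be qualified if the estimates differ materially across the three analyses.
6. Reconcile the 03/01 and 02/01 control windows. This has little effect on the bias, but the 02/01 version leaves the last month before VR start uncovered.

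The cost is one added date variable, modest extra analysis, and wider intervals in the added analyses: about 8% in (a) and 21% in (b). No extra patients or charts are needed.

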All patients will be admitted after surgery. It is anticipated that some subjects may opt to not continue with VR and withdraw from the study. Participants will be told that they may withdraw from the study at any time by reaching out to the PI, [name], or the study coordinator, [name]. Withdrawing from the study will not affect patient care. A patient may also decline participation for a VR session, but choose not to withdraw from the entire study. If a patient declines three consecutive VR sessions, then they will be withdrawn from the study. If a patient withdraws, any data already collected will be made de-identifiable and no further information will be collected. These patients will not be included in downstream analyses.

Retrospective Cohort:

These patients will not be approached for consent and therefore will not be able to withdraw from the study.

Study Procedures

Due to the limited number of corrective surgeries for scoliosis in a given year, a true randomized control trial cannot be performed. As such, a prospective cohort will be used – all patients undergoing surgery during the study period will be offered VR and will be assessed for pain, opioid usage, and mobilization following surgery. These outcome measures will be compared to data identified from a retrospective chart review of children receiving the same surgery but without an additional VR-intervention, thus serving as a historical control.

Prospective Arm:

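### The plan places no check of its device-related exclusions before the 5-minute headset trial, and patients who react to that trial drop out of the side-effect outcome

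*Combined protocol and SAP*

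**What the plan says.** All references are to the combined protocol and SAP.

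- **Inclusion/Exclusion Criteria.** The prospective arm is limited to idiopathic scoliosis. The exclusions include "History of seizures", head or neck surgery that makes a head-mounted display unsafe, and "Patients with vagal nerve stimulators, cardiac pacemakers, and/or cochlear implants that may receive interference from the VR device". Side effects during screening are a separate exclusion.
- **Sampling Method/Recruitment Process, prospective cohort.** All patients aged 13-18 having corrective scoliosis surgery "will be approached by a study team member during the pre-operative stage with information and consent documentation about the study". Those interested complete consent and HIPAA, in which "patients will consent to the study procedures as well as the research study team accessing their medical record for data collection". An entry in the enrollment log follows, and then: "During the consenting procedure, the patient will utilize the VR device for 5 minutes to screen for side effects". The only exclusion attached to that step is: "In the event that the patient experiences side effects during this 5-minute period, they will be excluded from the study".
- **Same section, retrospective sample.** These patients' "charts will be verified by a study team member to ensure they meet inclusion criteria". No matching sentence appears for the prospective arm.
- **Study Procedures.** The introduction says that "all patients undergoing surgery during the study period will be offered VR", without the word eligible. The prospective-arm text goes from consent to baseline pain and vital signs, and starts VR sessions on postoperative day 1.
- **Outcome Definitions/Data Points Collected.** Side effects of VR are a secondary outcome. The data list collects them from the VR sessions and includes seizures and loss of awareness.

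**The concern.** Two things are at stake.

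The first is participant protection. An exclusion that concerns wearing the device protects a patient only if it is applied before the device is worn. The plan sets out a sequence in some detail (approach, consent, log entry, headset) and has no step in it for checking these exclusions. The group approached is also wider than the group eligible, because neither the approach nor the offer of VR carries the limit to idiopathic scoliosis or to patients free of exclusions. The headset trial is itself a research procedure, and its timing relative to completed consent is left open.

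The second is statistical. A tolerance trial that removes everyone who reacts leaves a group selected for tolerance. If side effects are then counted only from the postoperative sessions, the reported rate describes that selected group and is lower than the rate among all patients who wore the device.

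**Working it through.** **Order of steps.** Reading the prospective-arm text from recruitment through Study Procedures:

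| Step | Check of seizure, implant or head/neck exclusions stated? |
|---|---|
| Approach all patients having corrective scoliosis surgery | No |
| Consent and HIPAA, including record access for data collection | No |
| Entry in enrollment log, subject number assigned | No |
| Headset worn for 5 minutes, during consenting | No; side effects only |
| Baseline pain and vital signs | No |
| VR sessions from postoperative day 1 | No |

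Past medical history is a listed data item, but no time is given for collecting it. The one described verification of charts against criteria belongs to the retrospective arm, where nobody wears a headset.

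**How many reach the step.** The accrual section gives 60-80 operations a year and about 40% declining:

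- 60 × 0.6 = 36
- 80 × 0.6 = 48

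The plan rounds this to 35-50 included. It subtracts nothing for ineligibility or for reactions to the headset, so 36-48 is really the number who agree, and each of them meets the 5-minute step as written.

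**Effect on the side-effect outcome.** Let N patients wear the headset in the trial, k react and are excluded, and s of the remaining N − k have a side effect in a later session.

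- Rate from sessions only: s/(N − k)
- Rate among all exposed: (s + k)/N
- Difference: (s + k)/N − s/(N − k) = (k/N) × [1 − s/(N − k)]

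Since s cannot exceed N − k, the difference is never negative. The sessions-only rate is too low whenever k is at least 1 and at least one remaining patient is free of side effects.

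The largest possible shortfall, at s = 0, is k/N. The documents give no value for k. For each patient excluded (k = 1):

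- N = 48: 1/48 = 2.1 percentage points
- N = 36: 1/36 = 2.8 percentage points

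The number of patients with a seizure history or a listed implant is not given either, so the number who might be wrongly exposed cannot be estimated.

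**The case against.** The strongest reply is that the gap is silence. Nothing says that the exclusions are checked after the headset, and staff may well ask about seizures, pacemakers or cochlear implants while the family is present. Consent forms were not available for review and the data collection tool appears only as an appendix title; either may contain a screening list. This stands, and it limits the point to what the visible text permits.

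It also rules out several stronger readings that a reader might infer:

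- *That the sections contradict each other on timing.* They do not. One lists exclusions and the other describes recruitment; neither says when the exclusions are verified.
- *That the 5-minute wear replaces the other exclusions.* Its stated purpose is to detect side effects and familiarise the patient, which serves one separate criterion.
- *That the headset precedes consent.* Consent and log entry are described first. The wording about the consenting procedure is ambiguous on whether consent is complete, and no more than that.
- *That eligibility cannot be checked until record access is granted.* Consent is the only authorisation described for this arm, but these exclusions can be asked of the family.
- *That reactions in the 5 minutes will certainly go unrecorded.* The plan does not say so. It ties collection to the sessions and does not say whether the trial wear counts as one.

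On the second part, one can argue that side effects among patients who pass a tolerance trial are a legitimate quantity. That is fair, but the outcome is stated simply as side effects of VR, without that restriction.

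The reply does not answer the central point. The plan writes down a device exposure and leaves the check that should guard it to unwritten practice.

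**Conclusion.** The point holds in this form. As written, the sequence allows a research exposure to the headset before any stated check of the plan's own device-related exclusions, and leaves open whether consent is complete at that moment. The approach and the offer of VR are also worded more widely than the eligibility criteria. Separately, the side-effect secondary outcome as described would omit patients who reacted in the 5-minute trial; the direction is towards understating side effects, by up to 2.1-2.8 percentage points for each patient so excluded.

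This rests on the visible text alone, on the plan's own figures for operations and refusals, and on reading the VR sessions as those that start on postoperative day 1. It does not affect sample size or the analyses of pain and opioid use. The change is worth making because the first part concerns the safety of minors and the second biases a named outcome, and both are cheap to put right.

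**What to change.** 1. Reconcile the exclusion list, the prospective recruitment text and the Study Procedures introduction. State that consent is complete and that the plan's existing exclusions have been verified and recorded, with the family, from the chart or both, before the 5-minute wear. Name who does this. No criterion needs to be added or altered.
2. Make the recruitment and Study Procedures text refer to eligible patients, including the limit to idiopathic scoliosis.
3. Record side effects and exclusions arising in the 5-minute wear, and report them alongside the side-effect outcome with all exposed patients as denominator. The rate from the postoperative sessions can still be shown, labelled as applying to patients who passed the trial wear.

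The cost is a few sentences in the protocol, one checklist line per patient, and a side-effect figure that may be slightly less favourable.
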